3.3 Secondary Endpoints

The secondary endpoint is ISTH major bleeding at 36 months (including procedural bleeding). This endpoint is defined as the Kaplan Meier estimates of time to first occurrence of major bleeding at 36 months and will be tested for non-inferiority of WATCHMAN to Control

3.3.1 Hypotheses

The objective of the secondary endpoint analysis is to test the null hypothesis that the difference in cumulative incidence between the Device and Control groups is greater than a prespecified noninferiority margin δ . The null hypothesis will be tested vs. the one-sided alternative hypothesis that the difference in cumulative incidence is less than a noninferiority margin δ .

H₀: $S_1(t) \ge S_0(t) + \delta$

 H_a : $S_1(t) < S_0(t) + \delta$,

where $S_1(t)$ and $S_0(t)$ are the Kaplan Meier estimates for cumulative incidence of all ISTH major bleeding at 36 months for the Device and Control groups, respectively.

3.3.2 Sample Size for Secondary Endpoint

The power and sample size were calculated using Farrington Manning methods for non-inferiority using SAS version 9.4. The assumptions and parameters pertaining to this design are as follows:

- Power = 84.3%
- Alpha = 0.025 (one-sided)
- Expected Device and Control group performance: cumulative incidence of 11% at 36 months in both groups
- A noninferiority margin $\delta = 5.25\%$
- Attrition: cumulative attrition rate of 20% in the Device Group and in the Control Group at 36 months.

The expected device time-to-event rate of 11% at 36 months was derived from subjects with previous ablations from the combined PROTECT AF, CAP, PREVAIL, and CAP2 studies' WATCHMAN arms. The observed event rate in these subjects was 13.6% event at 3 years. This rate is expected to be lower in the OPTION device arm due to enhanced implant experience over time, device improvements, and the use of direct oral anticoagulants post-implant rather than warfarin. The expected event rate in the Control group is expected to be similar to that of the Device group. The non-inferiority margin of 5.25% represents a relative risk of 1.48.

Given the above assumptions, 1280 subjects will be required. In order to account for up to 20% expected rate of attrition which includes subjects who die, withdraw or are lost-to-follow-up through 36 months without experiencing an endpoint event, a total of 1600 (1280/(1-0.2)) subjects need to be enrolled.

A sample size of 1600 subjects provides approximately 84% power for the secondary endpoint analysis.

In addition, the power and sample sizes have been re-evaluated for non-inferiority testing settings that would match the method described to perform the hypothesis analysis, namely differences in the Kaplan-Meier event rates of the respective endpoints using the Greenwood formula.

The operating characteristics of the statistical test for the primary effective endpoint, and the secondary endpoint, are calculated by simulating 10,000 trials, for each endpoint, for a given sample size using custom-written code in SAS. The results are consistent with the sample size calculation performed using a parametric formula, namely the Farrington-Manning method above. The table below presents the simulation results for the secondary safety endpoint.

Method	Farrington-Manning	Simulation	
Power	84.3%	88.9%	
Alpha (Type I error)	0.025	0.0254	

3.3.3 Statistical Methods for the Secondary Endpoint

All subjects in the randomized cohort will be included in the analysis. The secondary endpoint event from the WATCHMAN Device and Control arms, $S_1(t)$ and $S_0(t)$ at 36 months, defined as the 1095^{th} day post-randomization, will be estimated by the Kaplan Meier method. The 97.5% one-sided upper bound of confidence limit of the difference between WATCHMAN FLX and Control rates at 36 months will be calculated using the Greenwood formula for the variance of the Kaplan Meier estimates. The objective is met if this confidence limit is less than the predefined noninferiority margin of 5.25%.

3.3.4 Superiority Test for the Secondary Endpoint

If the non-inferiority hypothesis objective is met and the observed event rate favors the device arm, i.e., $S_1(t) < S_0(t)$, a superiority test will be subsequently performed and a one-sided p-value of 0.025 will be considered significant. No multiplicity adjustment is needed.¹

3.3.5 Multiplicity Consideration

The strategy to avoid the multiplicity issue for the additional tests is to have a hierarchical order for the hypothesis tests and the testing significance level [1] for all hypothesis testing is one-sided alpha 0.025. The hypothesis testing will follow the order below.

- 1. Superiority testing of the primary safety endpoint and non-inferiority testing of the primary efficacy endpoint,
- 2. Non-inferiority testing of the secondary endpoint,
- 3. Superiority testing of the secondary endpoint and
- 4. Superiority testing of the primary efficacy endpoint.

The study is successful if Superiority testing of the primary safety endpoint and non-inferiority testing of the primary efficacy endpoint are met.

3.3.6 Statistical Methods

The primary efficacy endpoint and the secondary endpoint event rate, $P_1(t)$ and $P_0(t)$, respectively, will be estimated by the Kaplan Meier method. The timepoint of 36 months is defined as the 1095^{th} day post-randomization. The 97.5% one-sided upper bound of confidence limit of the difference between Watchman FLX and Control rates will be calculated using Greenwood's formula for the variance of the Kaplan Meier estimates. The objective is met if this confidence limit is less than the predefined noninferiority margin of 5.0% for the primary effectiveness endpoint and 5.25% for the secondary endpoint.

In addition, calculation of an approximate p-value can be obtained. The critical value will be generated using the Com-Nougue approach to estimate the Z-statistic with Greenwood formula for estimating the variance.

The 97.5% one-sided confidence interval for event rate difference is

$$P_1(T) - P_0(T) \pm z_{1-\alpha/2} \sqrt{var(P_1(T)) + var(P_0(T))}$$

and

$$Z = \frac{P_1(T) - P_0(T) - \delta}{\sqrt{var(P_1(T)) + var(P_0(T))}}$$

P-value=1-probnorm(Z)

where for each treatment group (1=Device, 0=Control)

 $P_1(T)$, $P_0(T)$ = Kaplan Meier estimator of event rate at time t=T=1095 day

 δ = non-inferiority margin

Var= σ^2 =variance of the estimator where

$$\sigma$$
 = standard error by Greenwood's formula = $S(T)$
$$\sum_{j=1}^{T=1095} \frac{d_j}{n_j s_j}$$
,

S(T)=KM freedom from event estimate at time t=T

$$P_i(T)=1-S(T), i=0,1$$

n = number of subjects

d = number of events

s=n — d for the jth event time interval

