13.3.10. Changes to Planned Analyses

Any changes to the planned statistical analyses made prior to performing the analyses will be documented in an amended Statistical Analysis Plan approved prior to performing the analyses. Changes from the planned statistical methods after performing the analyses will be documented in the clinical study report along with a reason for the deviation.

14. Health Economics Outcomes

A formal health economics analysis may be completed as part of this trial study, given meaningful clinical results are obtained. This will take into consideration any differences in survival, complication rates, quality of life, and resource utilization. The EQ-5D and SF-12 may be used to assess health utilities. We will capture health care utilization measures at all sites. These inputs may be used in health economics analysis performed.

15. Data Management

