3.1.1 Hypotheses

The objective of the primary efficacy endpoint analysis is to test the null hypothesis that the difference in cumulative incidence between the Device and Control groups is greater than a prespecified noninferiority margin δ . The null hypothesis will be tested vs. the one-sided alternative hypothesis that the difference in cumulative incidence is less than a noninferiority margin δ .

 $H_0: S_1(t) \ge S_0(t) + \delta$

 H_a : $S_1(t) < S_0(t) + \delta$,

where $S_1(t)$ and $S_0(t)$ are the Kaplan Meier estimates for the cumulative incidence of stroke (including ischemic and/or hemorrhagic), all-cause death, and systemic embolism at 36 months for the Device and Control groups, respectively.

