                        event = 0;
                        time = t + 0.001;
                  end:
                  else do:
                        event = raw_event;
                        time = raw time;
                  end:
                                if time<=t and event=0 then censor=1; else censor=0;
            output;
            end:
```

```
end;
run:
option nonotes;
ods exclude all;
proc lifetest data=sim_SE1 outsurv=temp1_surv stderr ;
        strata grp;
     time time*event(0);
run;
ods exclude none;
option notes;
data temp2 surv;
     set temp1_surv;
      retain F SE;
      if survival ne . then F = 1 - survival;
      if SDF_STDERR ne . then SE = SDF_STDERR;
run;
data surv SE1;
     set temp2_surv;
      by study grp;
      if last.grp;
proc transpose data=surv_se1 out=surv_se_t1 prefix=f;
 by study;
 var f;
 id grp;
proc transpose data=surv_se1 out=surv_se_t2 prefix=se;
 by study;
 var se;
 id grp;
run;
data sim final;
 merge surv_se_t1 surv_se_t2;
 by study;
  * calculate the upper 97.5% CI and determine if it's less than the NI margin;
 uci = (f1-f2) + 1.96*sqrt(se1**2+se2**2);
 pass = (uci < &NI); *PASS := Power;</pre>
run;
proc means data=sim final n mean maxdec=3;
      var pass ;
          *output out=sim finalo;
      title1 'Endpoint Power';
         title2 'N=number of simulations, MEAN=Power';
run:
```

```
Primary Effectiveness NI Type I error Simulations.sas
Simulate [power and] type I error for a 2-arm study testing NI of treatment vs control
       Uses the KM event rates and Greenwood SE estimates in the Wald formula for testing NI in
binary event rates. ***/
***Type I Error Simulation Study
Type I error is assessed by setting the true rate for the treatment group to be equal to the
respective noninferiority margin, i.e. on the boundary of the null hypothesis parameter space,
where the type I error rate is maximized. This means the probability of success for the treatment
group was calculated as follows: p_T = p_C + \delta (\delta defined as noninferiority margin);
option compress=yes;
proc datasets library=work kill; run; quit;
let ni = 0.05;
                                       * NI margin for difference in event rates;
%let nsim = 10000;
                                       * number of simulated studies;
data sim SE1;
      seed =20121217; * Seed; *Seed1 and Seed2 necessary for grp1;
      seed2=20121218; * Seed; *Seed1 and Seed2 necessary for grp2;
      t = 3;

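### SAP 3.3.6 gives the supplementary non-inferiority p-value for the wrong tail: it should be probnorm(Z), not 1 − probnorm(Z)

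*SAP*

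**What the plan says.** SAP 3.3.6 covers the two non-inferiority endpoints, primary efficacy and secondary (ISTH major bleeding). P₁ and P₀ are Kaplan-Meier event rates at day 1095, and the arms are coded by "where for each treatment group (1=Device, 0=Control"). The decision rule uses the 97.5% one-sided upper limit of the Device-minus-Control difference: "The objective is met if this confidence limit is less than the predefined noninferiority margin of 5.0% for the primary effectiveness endpoint", with 5.25% for the secondary endpoint.

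The section then offers a p-value as an extra: "In addition, calculation of an approximate p-value can be obtained". It uses Z = (P₁ − P₀ − δ)/SE with Greenwood variances and ends with "P-value=1-probnorm(Z").

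The hypotheses in SAP 3.1.1 set the direction, with the "one-sided alternative hypothesis that the difference in cumulative incidence is less than a noninferiority margin". SAP 3.3.1 states the same direction for the secondary endpoint.

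**The concern.** Higher P means more events. The margin is subtracted from Device minus Control, so the better Device does, the more negative Z becomes. A p-value for the alternative P₁ < P₀ + δ must therefore shrink as Z falls. The printed formula does the opposite: it moves towards 1 as Device improves and becomes small only when Device is worse than Control by well over the margin.

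What is at stake is the reported p-value for the primary efficacy and secondary endpoints. If it is programmed as written, a correct finding of non-inferiority would appear beside a p-value that contradicts it. Correcting the formula after results are known would be an unplanned change to a primary-endpoint output.

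**Working it through.** **1. The plan's own figures, to confirm the setting.** Farrington-Manning, one-sided alpha 0.025:

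- Primary: 680 per arm, 10% in both arms, margin 5 points. Power is 85.88% (SAP 3.1.2: 85.9%), and 1360/0.85 = 1600.
- Secondary: 640 per arm, 11% in both arms, margin 5.25 points. Power is 84.33% (SAP 3.3.2: 84.3%), and 1280/0.80 = 1600.

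The SAP's Kaplan-Meier/Greenwood simulation was rebuilt with 10,000 trials, 800 per arm, and exponential events and attrition:

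- Power is 89.0% and 88.4% (SAP: 89.3% and 88.9%).
- Type I error is 0.027 and 0.026 (SAP: 0.024 and 0.0254).
- These differences are within simulation error.

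**2. The rule in terms of Z.** The rule is met when P₁ − P₀ + 1.96·SE < δ. Subtracting δ and dividing by SE gives Z < −1.96. The SAS code in SAP section 10 applies this rule: it adds 1.96 standard errors to the difference and passes if the result is below the margin. At the boundary Z = −1.96:

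- printed: 1 − Φ(−1.96) = 0.975
- lower tail: Φ(−1.96) = 0.025

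So whenever the rule is met, the printed p-value exceeds 0.975.

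**3. Size at the design values.** The asymptotic Greenwood variance per arm is

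S² · λ · (exp((λ + a)·3) − 1) / ((λ + a)·n)

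with S = 1 − F, λ = −ln(1 − F)/3, a = −ln(1 − attrition)/3 and n = 800. Attrition is 15% (primary) and 20% (secondary), as in the SAP code.

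- *Primary, F = 10%.* λ = 0.03512, a = 0.05417, and exp((λ + a)·3) = 1/(0.90 × 0.85) = 1.3072. Variance per arm = 0.81 × 0.03512 × 0.3072/(0.08929 × 800) = 0.0001223. SE of the difference = √(2 × 0.0001223) = 1.564%. Z = −5/1.564 = −3.20.
- *Secondary, F = 11%.* The same steps give SE = 1.658% and Z = −5.25/1.658 = −3.17.

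| Endpoint | Device / Control | SE (%) | Z | Upper limit (points) | Rule | Printed p | probnorm(Z) |
|---|---|---|---|---|---|---|---|
| Primary | 9% / 10% | 1.529 | −3.925 | 2.00 | met | 0.99996 | 0.00004 |
| Primary | 10% / 10% | 1.564 | −3.197 | 3.07 | met | 0.9993 | 0.0007 |
| Primary | 11% / 10% | 1.598 | −2.503 | 4.13 | met | 0.994 | 0.006 |
| Primary | 12% / 10% | 1.631 | −1.840 | 5.20 | not met | 0.967 | 0.033 |
| Secondary | 10% / 11% | 1.624 | −3.849 | 2.18 | met | 0.99994 | 0.00006 |
| Secondary | 11% / 11% | 1.658 | −3.167 | 3.25 | met | 0.9992 | 0.0008 |
| Secondary | 12% / 11% | 1.690 | −2.515 | 4.31 | met | 0.994 | 0.006 |
| Secondary | 13% / 11% | 1.721 | −1.888 | 5.37 | not met | 0.971 | 0.029 |

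The printed p-value falls as Device gets worse. With Control at 10% it is still 0.048 when Device is at 18%, and it is below 0.025 by 19% (Z = 2.20, p = 0.014).

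**4. Agreement with the rule across simulated trials.** Under the design assumptions, probnorm(Z) < 0.025 matched the confidence-limit rule in 100% of trials for both endpoints. The printed p-value fell below 0.025 in 0.0% of them and agreed with the rule in only 11.0% (primary) and 11.7% (secondary), which are the trials where both failed.

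**The case against.** The strongest reply concerns weight. The p-value is optional and approximate, and non-inferiority is decided only by the upper limit, which is stated correctly in SAP 3.1.3, 3.3.3 and 3.3.6 and coded correctly in all four attached programs. None of those programs computes this p-value, so nothing shows the error being carried into code. A value of 0.9993 beside an upper limit of 3.07 points against a 5-point margin would be conspicuous, and SAP section 6 requires reports to be validated. All of this stands and limits the consequence. It does not make the formula right, and validation against the SAP text could simply reproduce it.

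A second reply is that a symbol may have been lost. In the text as we could read it, the Greenwood standard error in the same block shows no square root, so an absolute value around Z might also be missing. 1 − Φ(|Z|) does equal Φ(Z) for every negative Z, which covers every row of the table. This cannot be fully excluded. But the p-value line is legible plain text with no visible gap, and an absolute value would still be wrong for positive Z: beyond 1.96 it would give p < 0.025 for a device clearly worse than the margin.

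**Conclusion.** The formula is wrong as written. For the Z and the alternative that the SAP defines, the p-value is probnorm(Z). The printed version is its complement and exceeds 0.975 whenever non-inferiority is met: at the design values, 0.9993 against 0.0007 (primary) and 0.9992 against 0.0008 (secondary).

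The direction of the error follows from the SAP's definitions alone. Only the worked p-values depend on assumptions: 800 per arm, exponential events and attrition, and the SAP's design rates. The effect is confined to the reported non-inferiority p-values. The decision rule, sample size, power and type I error stand. It should be corrected, but it does not threaten the trial's conclusions.

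**What to change.** In SAP 3.3.6, replace the last formula with P-value = probnorm(Z). Reversing the sign of Z and keeping 1 − probnorm would be equivalent, but only one of the two changes should be made.

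Optionally, for clarity only, write the bound in the same edit as the upper limit P₁ − P₀ + 1.96·SE. The 97.5% one-sided label, SAP 4.4 and the attached code already fix that multiplier.

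The cost is one line. Protocol 13.3.10 provides the route: "Any changes to the planned statistical analyses made prior to performing the analyses will be documented in an amended Statistical Analysis Plan". SAP 5.10 mentions only documentation in the study report, so the correction is best made before the analysis and can be bundled with any other SAP edits. It needs no protocol amendment and no change to alpha, margins, sample size or the decision rule.

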All time-to-event endpoints will be summarized using Kaplan-Meier methodology, and the time-to-event curves will be compared across treatment groups using a log-rank test. For the analysis of post-procedural major bleeding, the start time of follow-up in the Device group will be the day following the implant attempt, with the start time of follow-up in the Control being the day of randomization. In addition, the proportion of all strokes that are disabling will be compared across treatment groups using an exact binomial test.

All additional endpoint analyses will be exploratory in nature with no multiplicity adjustments, and will be analyzed once, at the time of primary efficacy and primary safety endpoint analyses.

4.2 Handling of Crossover

Control subjects will be allowed to "crossover" and receive a WATCHMAN device only after experiencing a primary efficacy or primary safety event endpoint event. These subjects will be censored from all analyses on the day after the event occurred. The primary efficacy and primary safety endpoints analysis will not be affected by this crossover as it uses time-to-event methodology, i.e. subjects no longer contribute to the analysis after experiencing an event. This is also true for any additional endpoint analysis that involves death, ischemic stroke or systemic embolism. Control subjects who undergo any LAA closure procedure prior to experiencing a primary efficacy or primary safety event endpoint event will be included in all analyses per the intent-to-treat principle.

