11.16. Local Laboratory

This study requires a local laboratory. Appropriate local laboratory certifications and documentation records are required to be maintained and filed at the site in the Investigative Site File through the enrollment period of the study.

12. Control Group Crossover

Subjects randomized to the Control Group that experience a primary efficacy endpoint event (stroke [including ischemic and/or hemorrhagic], systemic embolism) or primary safety event (ISTH major bleeding, or clinically relevant non-major bleeding) may be given the option of receiving a WATCHMAN FLX device prior to study completion. Crossing over without having experienced an endpoint event is discouraged. For those subjects that crossover, the Investigator should take into account the subject's individual risk/benefit profile when determining the timing of implantation after the primary endpoint event and associated medication.

Control Group subjects that receive any LAAC device will continue to be followed as Control Group subjects according to the intention-to-treat principle and their assigned subject visit windows. WATCHMAN FLX Implant information, including any procedure/device related events, as well as LAA imaging (recommended 3-month and 12-month LAA imaging from date of implant) will be collected and reported separately from the Device Group data analyses.

13. Statistical Considerations

The following sections provide an overview of the statistical considerations for the OPTION study. Further details can be found in the Statistical Analysis Plan.

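### Control crossover: SAP 4.2 and Protocol Section 12 give different rules, and no planned analysis isolates the effect of closure before an event on the non-inferiority test

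*SAP*

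**What the plan says.** **Who may cross over.** SAP 4.2 states that Controls may "receive a WATCHMAN device only after experiencing a primary efficacy or primary safety event endpoint event". Protocol Section 12 (Control Group Crossover) says that Controls with a stroke, a systemic embolism or a "primary safety event (ISTH major bleeding, or clinically relevant non-major bleeding) may be given the option of receiving a WATCHMAN FLX device", and then adds: "Crossing over without having experienced an endpoint event is discouraged". SAP Section 2 says the SAP is based on protocol version E, so the two rules should agree.

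**Closure before any event.** SAP 4.2 says that Controls who have an LAA closure "prior to experiencing a primary efficacy or primary safety event endpoint event will be included in all analyses per the intent-to-treat principle". Protocol Section 12 agrees: "Control Group subjects that receive any LAAC device will continue to be followed as Control Group subjects according to the intention-to-treat principle".

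**Crossover after an event.** SAP 4.2 says: "These subjects will be censored from all analyses on the day after the event occurred". It justifies this as follows: "The primary efficacy and primary safety endpoints analysis will not be affected by this crossover as it uses time-to-event methodology". Protocol Section 12 has no such censoring, and SAP 4.1 makes ITT the primary analysis for effectiveness.

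**Sensitivity set.** Treated as Assigned (SAP 4.1) censors Controls on the day of any LAA closure. On the Device side it keeps only successfully implanted subjects and starts their follow-up on the procedure day.

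**The concern.** Sites work from the protocol, under which an event-free Control can receive a device. Such a subject stays in Control but carries Device risk from then on. If the device is worse, the Control rate rises, the observed difference shrinks, and non-inferiority becomes easier to declare. The SAP's simulated type I error of 0.024 does not cover this, because its simulation code contains no crossover.

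The second problem concerns Controls who cross over after a bleed. A bleed is not a component of stroke, death or systemic embolism, so these subjects have not had an efficacy event. Removing them from the efficacy analysis the day after the bleed departs from ITT. It happens in the Control arm only, and it depends on what the subject later does.

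**Working it through.** **Inputs.** SAP 3.1.2: 10% at 36 months in both arms, margin 5%, one-sided alpha 0.025, 15% attrition, 1600 randomized. Allocation is 1:1, so 800 per arm. SAP 3.2.2: 20% Control bleeding at 36 months. Crossover rates, crossover times and post-bleed hazard ratios are assumptions, because the documents give none.

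**Reproducing the plan.** Farrington-Manning with 680 per arm gives 85.88% power (stated 85.9%). For the Kaplan-Meier test with exponential events (hazard λ = −ln(1−p)/3) and attrition (hazard λa = −ln(0.85)/3), the Greenwood variance per arm is

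V(p) = (1−p)²/800 × λ/(λ+λa) × [1/((1−p)×0.85) − 1].

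- V(0.10) = 0.0001223 and V(0.15) = 0.0001734.
- Power at 10% vs 10%: SE = √(2×0.0001223) = 0.01564, and Φ(0.05/0.01564 − 1.96) = 89.2% (the SAP's simulation gives 89.3%).
- SE at the margin, 15% vs 10%: √(0.0001734 + 0.0001223) = 0.0172. The false non-inferiority rate is 2.5% with no crossover.

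**Event-free crossover kept in Control.** Let a fraction c of Controls carry Device risk for a fraction f of follow-up, with the device truly at 15%. The Control rate is then 0.10 + 0.05cf, and the false non-inferiority rate is Φ(0.05cf/SE − 1.96), with the SE recomputed at the diluted Control rate.

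| c | f | Control rate | Apparent difference | SE | False non-inferiority |
|---|---|---|---|---|---|
| 2% | 0.5 | 10.05% | 4.95% | 0.01721 | 2.7% |
| 5% | 0.5 | 10.125% | 4.875% | 0.01724 | 3.0% |
| 10% | 0.5 | 10.25% | 4.75% | 0.01728 | 3.5% |
| 20% | 0.5 | 10.5% | 4.5% | 0.01735 | 4.7% |
| 5% | 1 | 10.25% | 4.75% | 0.01728 | 3.5% |
| 10% | 1 | 10.5% | 4.5% | 0.01735 | 4.7% |
| 20% | 1 | 11.0% | 4.0% | 0.01751 | 8.2% |

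Spreading crossover times uniformly over follow-up gives 2.7%, 3.0%, 3.5% and 4.8% at 2%, 5%, 10% and 20%, so the mid-follow-up rows are representative.

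**Bleed-triggered crossover censored the day after the bleed.** The number who could become eligible is about 0.20 × 800 = 160 Controls. Simulation (2,500 trials per setting) gives the following Control efficacy rates:

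- Post-bleed hazard ratio 2, implant one week after the bleed: true rate 10.9%; estimated 10.8%, 10.5% or 10.0% if 25%, 50% or all of those eligible cross over.
- Hazard ratio 3, same lag: true rate 11.8%; estimated 11.5%, 11.0% or 10.0%.
- Hazard ratio 1, implant six months after the bleed, all crossing: true rate 10.0%; estimated 10.3%, with false non-inferiority about 3.8% (Monte Carlo SE about 0.4 points).

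The bias can run either way. If bleeders are at higher risk, censoring removes high-risk follow-up and lowers the Control rate, which works against the device. If risk is unchanged but the implant comes later, only subjects who survived event-free to implant are censored back to the bleed. That raises the Control rate and favours non-inferiority.

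**The case against.** The strongest reply is that event-free crossovers already have a prespecified rule. Both documents keep them in Control under ITT, so the difference in permission wording does not change the primary analysis. That stands. So does the point that SAP 4.2 is not incoherent for stating a rule and then saying how departures from it are analysed.

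The trigger lists are also closer than they look. Protocol Section 12 does not repeat the non-procedural limit, but Protocol 13.1.2 defines non-procedural as after 3 days, and SAP 3.2 counts those days from randomization for Controls. At most, bleeds in a Control's first three days are in doubt.

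A third reply is that Treated as Assigned already censors Controls at closure. That stands only in part. It changes three things at once: Control censoring, the Device population and the Device time origin. A result that differs from ITT could not be attributed to crossover.

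The size is fairly contested too. The 8.2% figure needs a fifth of Controls to receive the device at time zero, and at 2% crossover the effect is negligible. The share of Controls eligible to cross over is not a crossover rate and does not measure bias.

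**Conclusion.** The concern holds in a limited form. The documents state two crossover rules and two ways of handling post-event crossovers, and both differences need reconciling. The pull of event-free crossover on the non-inferiority test is mildly anti-conservative: about 2.7% to 4.7% instead of 2.5% for 2% to 20% of Controls crossing at mid-follow-up. This rests on assumed crossover rates, exponential hazards, full Device risk after crossover and a device truly at the margin. No planned analysis isolates the effect.

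A reader might infer that the non-inferiority analysis is safe under the SAP's stricter wording and unsafe only under the protocol's. The documents do not support that. The stricter rule still admits crossover after a bleed, and SAP 4.2 censors those subjects while they remain at risk of stroke, death or systemic embolism. Its statement that the primary analyses are unaffected is true only when the qualifying event belongs to the endpoint being analysed. The direction of the resulting bias is not known in advance.

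**What to change.** 1. Reconcile SAP 4.2 and Protocol Section 12 to one crossover rule and one list of triggering events. Which rule is for the sponsor to decide.
2. In SAP 4.2, keep Controls who cross over after a bleed in the ITT efficacy analysis, and limit the sentence on unaffected primary analyses to qualifying events that are components of the endpoint being analysed.
3. Add one sensitivity run of the primary non-inferiority test. Keep all randomized Device subjects and the randomization time origin, and censor Controls at an LAA closure that precedes an event. State how a closure after a bleed but before an efficacy event is treated; censoring at the closure date, not the bleed date, avoids conditioning on later survival to implant.
4. Report the number, timing and reason of Control closures beside the ITT result.

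The cost is wording in two sections and one extra run. Protocol Section 12 already provides for collecting crossover implant information; the reason for closure may need a field if it is not captured. The downside is that the censored run assumes crossover timing is non-informative, so it should be read beside ITT and not replace it.

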13.2. General Statistical Methods

13.2.1. Analysis Sets

The primary analysis for each of the Primary and Secondary Endpoints will be performed on an intent-to-treat basis, with each subject analyzed as being part of their randomized group regardless of the actual treatment received. Additional analysis sets per actual treatment received will be performed for the Primary and Secondary Endpoints as sensitivity analyses.

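### SAP 4.2 censors Control crossovers for every endpoint the day after a qualifying event, so strokes, emboli and deaths after a bleed and crossover drop out of the primary efficacy analysis

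*SAP*

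**What the plan says.** SAP 4.2 allows a Control subject to receive the device after either a primary efficacy or a primary safety endpoint event. Protocol section 12 confirms the bleeding route: a Control subject with a "primary safety event (ISTH major bleeding, or clinically relevant non-major bleeding) may be given the option of receiving a WATCHMAN FLX device".

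For these subjects SAP 4.2 sets one rule across all endpoints: "These subjects will be censored from all analyses on the day after the event occurred". It then reassures the reader: "The primary efficacy and primary safety endpoints analysis will not be affected by this crossover as it uses time-to-event methodology". The reason given is that "subjects no longer contribute to the analysis after experiencing an event". Control subjects who receive a closure device without a prior endpoint event are treated the opposite way in the same section: they "will be included in all analyses per the intent-to-treat principle".

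Elsewhere the plan is plain intention to treat:

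- Protocol section 12: "Control Group subjects that receive any LAAC device will continue to be followed as Control Group subjects according to the intention-to-treat principle".
- Protocol 13.2.1: "The primary analysis for each of the Primary and Secondary Endpoints will be performed on an intent-to-treat basis".
- SAP 4.1 analyses primary efficacy by randomized group whatever treatment was received. It provides a separate treated-as-assigned set in which Controls are censored on the day of any closure procedure.
- SAP 7.3 censors event-free subjects at last follow-up in all time-to-event analyses.

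**The concern.** The stated reason holds only when the qualifying event belongs to the endpoint being analysed. A Control subject who has a stroke has indeed left the efficacy risk set. One who bleeds has not, because SAP 3.1 defines efficacy as first stroke, all-cause death or systemic embolism. If that subject later crosses over, follow-up for efficacy ends the day after the bleed, and a subsequent stroke or death is not counted.

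The same fault affects other endpoints. Bleeds after a stroke and crossover are lost from primary safety. Major bleeds after a clinically relevant non-major bleed and crossover are lost from the secondary endpoint. Deaths after a stroke and crossover are lost from the all-cause death analysis.

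The censoring is also informative by construction. It is dated at the bleed but triggered by a later decision. A bleeder who dies before an implant counts as an event, while one who survives to be implanted has the intervening event-free time erased. At stake is a co-primary comparison on which study success depends (SAP 3.3.5): the Control rate in the non-inferiority test would depend on unplanned crossover behaviour.

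**Working it through.** **Inputs from the documents.** 800 per arm (1600 randomized 1:1); 36-month efficacy rate 10% in both arms; margin 5 points; one-sided alpha 0.025; attrition 15% (SAP 3.1.2); Control bleeding 20% at 36 months (SAP 3.2.2).

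**Assumptions not in the documents.** The share of Control bleeders who cross over, the bleed-to-implant lag, and the hazard ratio (HR) for efficacy events after a bleed. All three are varied.

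**Step 1: reproduce the plan's figures.** Farrington–Manning power with 680 evaluable per arm is 85.88% (plan: 85.9%), and 1360/0.85 = 1600. Re-running the SAP's Kaplan–Meier/Greenwood simulation over 10,000 trials gives power 89.6% (plan: 89.3%) and type I error 0.0241 (plan: 0.024).

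**Step 2: who is exposed.** With 20% bleeding and 15% attrition, about 140 of 800 Controls bleed while still at risk for efficacy. The rule bites on those of them who cross over.

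**Step 3: large-sample effect on the Control rate.** Setup: 1.5 million simulated Controls, exponential times, overall efficacy rate held at 10.0%, 60-day lag, no attrition (so 800 × 10% = 80 expected events). Between 36 (25% crossing) and 72 (50% crossing) of 800 Controls are censored early. Power is Φ((0.05 − shift)/0.01564 − 1.96), where shift is the fall in the Control rate and 0.01564 is the standard error of the difference with 15% attrition. With no shift this gives Φ(1.237) = 89.2%.

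| HR after bleed | Share crossing | Events lost per 800 | Control rate under SAP 4.2 | Power |
|---|---|---|---|---|
| 1 | 25% / 50% | 1.8 / 3.6 | 10.03% / 10.05% | about 90% / 90% |
| 2 | 25% / 50% | 3.2 / 6.6 | 9.85% / 9.68% | 87% / 85% |
| 4 | 25% / 50% | 5.4 / 10.4 | 9.58% / 9.18% | 83% / 76% |

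For example, at HR 4 with 50% crossing the shift is 0.82 points, and (0.05 − 0.0082)/0.01564 − 1.96 = 0.713, so power is 76%. Repeat runs agree to within about 0.05 point on the Control rate.

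**Step 4: trial-level simulation with attrition.** Setup: 3,000 trials per scenario, 3-month lag, about 74 Control efficacy events under intention to treat, power about 89%.

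| HR after bleed | Share crossing | Events lost | Control rate | Power |
|---|---|---|---|---|
| 1 | 25% / 50% | 1.6 / 3.1 | 10.03% / 10.07% | 89% / 89% |
| 2 | 25% / 50% | 2.7 / 5.5 | 9.87% / 9.75% | 87% / 86% |
| 3 | 25% / 50% | 3.7 / 7.3 | 9.71% / 9.49% | 85% / 82% |

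The extremes are 0.6 events lost (10% crossing, HR 1, 3-month lag) and 17.5 lost (100% crossing, HR 3, no lag). In the latter the Control rate is 8.4% and power 59%.

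**Step 5: the opposite direction.** At HR 1 the backdating alone raises the Control rate, because event-free time before the implant is discarded. At 100% crossing with a 3-month lag it goes from 10.0% to about 10.2%. The standard error at the null boundary (15% against 10%) is 0.0172. The 0.03–0.07 point rise at 25–50% crossing therefore moves one-sided type I error from 0.025 to about Φ(−1.96 + 0.0003/0.0172) = 0.026 up to Φ(−1.96 + 0.0007/0.0172) = 0.027.

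**The case against.** The best counter-argument concerns severity. Wherever bleeding worsens prognosis in these calculations, the Control rate falls and non-inferiority becomes harder to show. The rule then costs the sponsor power and does not manufacture a false success. The reverse bias appears only when bleeding has no prognostic weight, and it is small. The crossover share and the hazard ratios are not documented, and an HR of 4 is severe for a bleeding category that includes non-major bleeds needing only a face-to-face evaluation. SAP 5.6 already promises a sensitivity analysis of censored data with a worst case, and SAP 5.5 a tipping-point analysis for attrition. Finally, SAP 4.1 states intention to treat for this very endpoint, so 4.2 may be a drafting slip and not a decision to abandon it.

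Much of this stands. The size is unknown, the fourfold-hazard figures are the upper part of the range examined at 25–50% crossing, and only bleeders who go on to cross over are affected. It does not rescue the rule. Sensitivity analyses do not repair the primary estimate. Direction is not assured either, since none of the calculations allows crossovers to be healthier or sicker than other bleeders. And if 4.1 and 4.2 conflict, two analysts could each follow the SAP and report different Control rates from the same data.

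**Conclusion.** The concern holds, and SAP 4.2 must be corrected. The no-effect statement is false for any crossover triggered by an event outside the endpoint being analysed. The censoring rule contradicts Protocol sections 12 and 13.2.1, SAP 4.1, and the last sentence of SAP 4.2 itself.

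The qualitative finding needs no assumption beyond some Control bleeders crossing over. The size does. At 25–50% crossing, a doubled hazard after a bleed costs roughly 2 to 4 points of power and a fourfold hazard roughly 6 to 13. With no added hazard, the Control rate rises by less than 0.1 point.

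**What to change.** In SAP 4.2, delete the sentence that censors crossovers and the statement that the primary analyses are unaffected. Replace them with wording such as: Control subjects who receive any LAAC device, before or after an endpoint event, remain in the Control arm without censoring in all intention-to-treat analyses.

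Keep censoring at crossover only in the treated-as-assigned analysis of SAP 4.1, dated at the closure procedure and not at the earlier event.

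In the same edit, state which set governs primary safety. The end of SAP 4.1 ties it to treated-as-assigned, while SAP 3.2.3 and Protocol 13.2.1 point to all randomized subjects. Until that is settled, crossover handling for bleeding stays ambiguous.

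The cost is SAP wording only. Under Protocol section 12 these subjects "will continue to be followed as Control Group subjects according to the intention-to-treat principle", so the plan already calls for the follow-up data needed.
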